3 LIST OF ABBREVIATIONS

Abbreviation	Definition
ANCOVA	analysis of covariance
CGI-I	Clinical Global Impression of Improvement
CGI-S	Clinical Global Impression of Severity
ET	end of treatment
eCRF	electronic case report form
HADS	Hospital Anxiety and Depression Scale
HAM-A	Hamilton Anxiety Rating Scale
HAMD-17	Hamilton Depression Rating Scale - 17-item Version
LOCF	last observation carried forward
MDD	major depressive disorder
MMRM	mixed-models repeated measures
SAP	statistical analysis plan
SDS	Sheehan Disability Scale
SHAPS	Snaith-Hamilton Pleasure Scale

Table 1List of Abbreviations

4 INTRODUCTION

Detailed descriptions of the methods and presentation of data analyses proposed for BlackThorn Therapeutics, Inc. Protocol K2-MDD-201 (A Phase 2a, Randomized, Double-blind, Placebo-controlled Proof of Concept Study to Evaluate the Effects of Oral BTRX-335140 Versus Placebo in Subjects With Major Depressive Disorder) Amendment 7 Version 8.0 (24 January 2022) are described in the original statistical analysis plan (SAP), version 2.0, 03 June 2022 (hereafter referred to as "the main SAP").

The purpose of this addendum is to provide clarifications to the definitions and methodology related to the analyses described in the main SAP.

5 STATISTICAL METHODS

5.1 General Methodology

5.1.1 Analysis Visit Window

For efficacy and safety analyses by visit, assessments at scheduled and unscheduled visits will be mapped to the appropriate analysis window as detailed in Table 3 and Table 4 of the main SAP. The analysis visit windows for the standard ophthalmologic examination at Visit 3 (Week 2) and Visit 4 (Week 4) from Table 4 of the main SAP will instead be mapped as shown in Table 2.

Table 2Analysis Windows for Standard Ophthalmologic Examination by
Visit

Period	Screening	Baseline	s	tudy Drug	Treatme	nt	Safety F up	'ollow-
Visit	1	2	3	4	5	6		
	Days -7 to -28	Day 1	Day 15 (±2 d)	Day 29 (±2 d)	Day 43 (±2 d)	Day 57 (±2 d)	Day 71	Day 85
Analysis Visit Name		Baseline	Week 2	Week 4	Week 6	Week 8	Week 10	Week 12
Standard ophthalmologic examination	NA	≤ 1 Pre- dose	[2, 14]	NA	NA	≥ 15	NA	NA

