- ^g At Screening, collect height for BMI calculation.
- ^h Ophthalmologic examinations will be performed by a site-affiliated ophthalmologist. Details for the standard ophthalmologic examination and corneal specular microscopy will be described in a separate ocular monitoring manual. Additional standard ophthalmologic exams and / or corneal specular microscopies may be conducted to assess subject safety.

BTRX-335140 Clinical Study Protocol Amendment 7

- ⁱ Baseline ophthalmologic examinations (standard and corneal specular microscopy) must be performed before randomization.
- ^j Prior to Visit 3 (Week 2) (between Days 7 and 14 [+2 days]), a standard ophthalmologic examination will be performed.
- ^k Serum pregnancy test is to be performed at screening visit only and urine pregnancy tests will be performed by the site at all subsequent visits.
- ^m Optional assessment; subject refusal to perform will not prohibit study participation.
- ⁿ Unscheduled hepatic monitoring testing may be performed at any time on the basis of clinical laboratory testing results, after consultation with the Sponsor-designated medical monitor (see Section 6.3.2.2).
- ^o The C-SSRS Baseline version will be used at Screening and "Since Last Visit" version will be used for all subsequent visits.
- ^p Adverse events reported before first dose of study drug to be recorded as medical history. Serious AEs will be recorded on the AE eCRF from the time of informed consent.
- ^q Subjects will be instructed to take their study drug daily in the morning and preferably with food.
- ^r Subjects will take their first dose of study drug (BTRX-335140 or placebo) under the supervision of clinical study personnel during the baseline visit.
- s
- ^t The Week 12 corneal specular microscopy should be completed for all subjects (ie, completers and early termination) unless consent is withdrawn. The corneal specular microscopy should be conducted approximately 12 weeks after the first dose of study drug; exceptions to be discussed with the medical monitor.

BTRX-335140	BlackThorn Therapeutics, Inc.
Clinical Study Protocol Amendment 7	Date: 24Jan2022

TABLE OF CONTENTS

CL	INICAL ST	TUDY PROTOCOL: K2-MDD-201	1
SP	ONSOR SI	GNATURE	2
IN	VESTIGAT	FOR AGREEMENT	3
SU	MMARY (OF CHANGES	4
SY	NOPSIS		5
SC	HEDULE (OF PROCEDURES AND ASSESSMENTS	11
TA	BLE OF C	ONTENTS	14
LIS	ST OF TAE	BLES	
LIS	ST OF FIG	URES	
LIS	ST OF APP	ENDICES	
LIS	ST OF ABE	BREVIATIONS	19
1	IN	TRODUCTION	
	1.1	Background Information	

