7.2 Visit 2: Baseline (Day 1)

The following order of procedures is recommended to prioritize eligibility and safety assessments:

- 1. Breathalyzer test for blood alcohol level
- 2. Subject and investigator will complete the following study eligibility criteria on the tablet supplied:
 - a. HAMD-17
 - b. HAM-A
 - c. Allow subject to complete SHAPS; reviewed by site personnel qualified to oversee completeness
 - d.

BTRX-335140	BlackThorn Therapeutics, Inc.
Clinical Study Protocol Amendment 7	Date: 24Jan2022

- e. C-SSRS 'Since Last Visit' version
- f.
- g. Allow subject to complete HADS; reviewed by site personnel qualified to oversee completeness
- h. Allow subject to complete SDS; reviewed by site personnel qualified to oversee completeness
- i. CGI-I and CGI-S
- j.
- 3. Concomitant therapies review and reporting
- 4. Physical examination if indicated
- 5. Weight
- 6. Vital signs (respiratory rate, BP, and pulse [supine and standing]; temperature)
- 7. COWS
- 8. 12-lead ECG
- 9. Urine drug screen for all subjects and urine pregnancy test for women of child-bearing potential

The investigator will confirm the subject's eligibility prior to completing the remaining randomization visit procedures. After confirmation, it is recommended that the remaining procedures be completed in the following order:

- 1. Complete randomization via IWRS
- 2. Collect blood and urine samples for central laboratory analysis,
- 3. Dispense allocated study drug, and instruct subject on the importance of compliance and returning the dispensed bottle with any unused study drug at each visit. Instruct all subjects to take 1 capsule of their assigned study drug daily in the morning and preferably with food; administer the first dose of study drug, which should be taken under the supervision of clinical study personnel. It is recommended that subjects remain in the clinic for 1 hour after taking study drug.
- 4. AE reporting

The investigator will review the results of the central laboratory tests for safety prior to the next visit.

Prior to Visit 3 (Week 2) (between Days 7 and 14 [+2 days]), a standard ophthalmologic examination should be performed (refer to the Schedule of Procedures and Assessments, footnote "j" and Section 6.3.6).

BTRX-335140	BlackThorn Therapeutics, Inc.
Clinical Study Protocol Amendment 7	Date: 24Jan2022

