7.6 Visit 6: Week 8 (Day 57)/End of Treatment

Special effort will be made by the site to encourage subjects who discontinue from the study early to complete all Visit 6 (Week 8) safety assessments (within 2 days of their last dose of study drug), the Safety Follow-up TC, and ophthalmologic examinations (Section 7.8); efficacy assessments are to be performed only if the subject has remained on study drug. If the subject does not attend the discontinuation visit, the C-SSRS should be completed if the site has become aware of a potential suicide-related thought or behavior by other communications.

BTRX-335140	BlackThorn Therapeutics, Inc.
Clinical Study Protocol Amendment 7	Date: 24Jan2022

Additional ophthalmologic examinations (standard ophthalmologic exams and/or corneal specular microscopies) may be conducted to monitor subject safety.

The following order of procedures is recommended to prioritize safety and efficacy assessments:

- 1. Breathalyzer test for blood alcohol level
- 2. Subject and investigator will conduct/administer the following assessments on the tablet supplied:
 - a. HAMD-17
 - b. HAM-A
 - c. Allow subject to complete SHAPS; reviewed by site personnel qualified to oversee completeness
 - d. e.
 - f. Allow subject to complete HADS; reviewed by site personnel qualified to oversee completeness
 - g. Allow subject to complete SDS; reviewed by site personnel qualified to oversee completeness
 - h. C-SSRS 'Since Last Visit' version
 - i. CGI-I and CGI-S
 - j. k.
- 3. Concomitant therapies review and reporting
- 4. AE reporting
- 5. Physical examination if indicated
- 6. Weight
- 7. Vital signs (respiratory rate, BP, and pulse [supine and standing]; temperature)
- 8. COWS
- 9. 12-lead ECG
- 10. Standard ophthalmologic examination (± 2 days) (refer to Section 6.3.6)
- 11. The subject-returned investigational study drug will be accounted for.
- 12. Complete IWRS

BTRX-335140	BlackThorn Therapeutics, Inc.
Clinical Study Protocol Amendment 7	Date: 24Jan2022

13. Blood and urine collection for central laboratory analysis (including urine drug screen for all subjects and urine pregnancy test for women of child-bearing potential)

14.

The investigator will review the results of the central laboratory tests for safety in a timely manner.

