5.3 Safety Evaluation

5.3.1 Vital Signs, Physical Findings, and Other Observations Related to Safety

5.3.1.1 Ophthalmology Examination

The main SAP states "Standard ophthalmologic examination and corneal specular microscopy examination results will be summarized by presenting shift from baseline to end of study results as normal, abnormal not clinically significant, and abnormal clinically significant." This summary will be presented by visit.

Additionally, the subjects who have endothelial dystrophy medical history prior to treatment used for the subgroup analysis will be identified by having a preferred term of "Corneal Dystrophy" collected on the Medical and Psychiatric History Other Than MDD (major depressive disorder) electronic case report form (eCRF) prior to date of first dose of study drug.

DocuSign[•]

Certificate Of Completion		
Envelope Id: B873441E0C1E48ED881DC6068D760 Subject: Complete with DocuSign: BlackThorn_K2-M Source Envelope:)AA4 MDD-201_SAP Addendum_v1.0_06OCT2022.docx	Status: Completed
Document Pages: 9 Certificate Pages: 6 AutoNav: Enabled Envelopeld Stamping: Disabled Time Zone: (UTC-08:00) Pacific Time (US & Canada	Signatures: 5 Initials: 0 a)	Envelope Originator:
Record Tracking		
Status: Original 10/6/2022 10:54:51 AM	Holder:	Location: DocuSign
Signer Events	Signature	Timestamp
Principal Biostatistician Precision for Medicine, Oncology and Rare Disease Security Level: Email, Account Authentication (Required)	Signature Adoption: Pre-selected Style Signature ID: 9E683A07-3C33-4051-A68D-48084B8342E1	Sent: 10/6/2022 10:59:24 AM Viewed: 10/6/2022 12:03:08 PM Signed: 10/6/2022 12:03:43 PM
	With Signing Authentication via DocuSign password With Signing Reasons (on each tab): I approve this document	
Electronic Record and Signature Disclosure: Not Offered via DocuSign		
[name]: Email, Account Authentication (Required)	DocuSigned by: Signer Name: Signing Reason: I approve this document Signing Time: 06-Oct-2022 J 2:25:56 PM PDT C73F6D48471248418A5BB7CF72546EDF Signature Adoption: Pre-selected Style	Sent: 10/6/2022 10:59:24 AM Viewed: 10/6/2022 2:25:43 PM Signed: 10/6/2022 2:27:18 PM
Electronic Record and Signature Disclosure: Accepted: 10/6/2022 2:25:43 PM ID: 44075589-189c-42ba-ad35-181a799bc7c1	Signature ID: C73F6D48-4712-4841-8A5B-B7CF72546EDF Using Signed using mobile With Signing Authentication via DocuSign password With Signing Reasons (on each tab): I approve this document	

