6.4.2.8 Ophthalmologic Examination

The following ocular assessments are performed, using these standard clinical operating procedures, at specified visits, on both eyes of each subject:

- 1. Standard Ophthalmologic Examinations: performed at Screening/Baseline, between post-dose days 7-15, and at end of treatment/Week 8.
- 2. Corneal Specular Microscopy (CSM): noncontact or contact specular microscopy for qualitative and quantitative examination of the central corneal endothelium (cell count, cell shape, density, and morphology), with image capture at Screening/Baseline and 12 weeks following first dose.

Local investigators assess and record the results of items 1 and 2 on the examination worksheet. For both the standard ophthalmologic examination and CSM, an assessment of normal/abnormal is captured as well as whether the abnormal result is clinically significant or not. CSM results are sent to **second second** where the designated ophthalmology expert will review. Additional ophthalmologic examinations (standard ophthalmologic exams and/or corneal specular microscopies) may be conducted at any time during the study to assess subject safety.

The final ocular examination for corneal specular microscopy is conducted approximately 12 weeks (+2 days) after the first dose of study drug (including both subjects who complete the study and subjects who discontinue early from the study).

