7.1.2 Analysis Visit Window

For efficacy analyses and safety analysis by visit, assessments at scheduled and unscheduled visits will be mapped to the appropriate analysis window as detailed in Table 3 and Table 4. In the event where more than one visit falls in the same analysis window, the following rules will be used in sequence to determine the record that will be analyzed:

- If there is a scheduled visit in the analysis window, then the scheduled visit's data will be used.
- If there is no scheduled visit in the analysis visit window, the data closest to the scheduled day/time visit will be used.
- If there is no scheduled visit in the analysis visit window and there is a tie between the visits with regards to the number of days/hours before and after the scheduled day, the later data will be used.

Visit windows will not apply to listings. All data will be included in subject listings.

Windowing will be applied to the data prior to any missing data calculations.

Confidential

Period	Screening	Baseline	Study Drug Treatment Safety Follow-up					ollow-up
Visit	1	2	3	4	5	6		
	Days –7 to –28	Day 1	Day 15 (±2 d)	Day 29 (±2 d)	Day 43 (±2 d)	Day 57 (±2 d)	Day 71	Day 85
Analysis Visit Name		Baseline *	Week 2	Week 4	Week 6	Week 8	Week 10	Week 12
CGI-I HADS	NA	≤1 Pre- dose	[2, 22]	[23, 36]	[37, 50]	[51, 71]	NA	NA
HAMD-17 HAM-A SHAPS		≤ 1 Pre-						
	NA	dose	NA	[16, 43]	NA	[44, 71]	NA	NA
CGI-S	NA	≤1 Pre- dose	NA	NA	NA	[44, 71]	NA	NA
SDS	NA	≤1 Pre- dose	NA	[23, 36]	[37, 50]	[51, 71]	NA	NA

Table 3Analysis Windows for Efficacy Analyses

* Baseline for analysis visit refers to baseline value for efficacy analysis defined in Section 7.1.5

Period	Screening	Baseline	s	Study Drug Treatment				ollow-
Visit	1	2	3	4	5	6		
	Days -7 to -28	Day 1	Day 15 (±2 d)	Day 29 (±2 d)	Day 43 (±2 d)	Day 57 (±2 d)	Day 71	Day 85
Analysis Visit Name		Baseline	Week 2	Week 4	Week 6	Week 8	Week 10	Week 12
Vital signs Clinical laboratory tests COWS	NA	≤1 Pre- dose	[2, 22]	[23, 36]	[37, 50]	[51, last dose +30]	NA	NA
Body weight ECG	NA	≤1 Pre- dose	NA	[2, 43]	NA	[44, last dose +30]	NA	NA
Standard Ophthalmologic examination	NA	≤1 Pre- dose	NA	[2, 14]	NA	≥ 15	NA	NA
Corneal specular microscopy	NA	≤1 Pre- dose	NA	NA	NA	NA	NA	≥2
C-SSRS	Nominal	≤ 1 Pre- dose	[2, 22]	[23, 36]	[37, 50]	[51, 64]	[65, last dose +30]	NA

Table 4Analysis Windows for Safety Analyses by Visit

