7.1.4 Standard Calculations

Where appropriate, the calculated study day of each assessment or event will be presented with the assessment or event date on subject data listings, where study day will be determined as:

- The assessment/event date minus the date of first dose of study drug, if the assessment/event date is prior to the date of first dose; and
- The assessment/event date minus the date of first dose of study drug, plus one, if the assessment/event date is on or after the date of first dose.

Start and stop dates will be imputed when partial dates are present as needed to determine treatment emergent events and concomitant medications/procedures. No imputation will

be done for a completely missing start/stop date or for subjects who did not receive study treatment.

Start dates with a missing day but which have month and year provided will be imputed such that:

- If the provided month and year match the month and year for that subject's first dose date, then the Day 1 date will be used
- In all other cases the 1st of the month will be used with the provided month and year

Start dates with a missing day and month but which have year populated will be imputed such that:

- If the provided year matches the year for that subject's first dose date, then the first dose date will be used
- In all other cases the 1st of January will be used with the provided year

Stop dates will be imputed as follows:

- Missing day with a provided year and month will use the last day of the month
- Missing day and month with provided year will use December 31

If the imputed stop date is greater than the last study date for the subject, then the imputed date will be replaced with the last known subject date.

The date of the start of the current depressive episode and date of diagnosis of MDD will be imputed when the month or day are missing as follows:

- Missing day is set to 1 if the same year and month as the date of assessment. Otherwise it is set to 15
- Missing month and day are set to Jan 1 if the same year as the date of assessment. Otherwise it is set to July 1.

Other variables requiring calculations will be derived using the following formulas:

- **Days:** A duration between two dates expressed in days will be calculated using the following conventions:
 - Later date earlier date + 1, if the earlier date is on or after the date of first dose of study drug; or

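### SAP Addendum Table 2 closes the Week 2 window for the standard eye examination on Day 14, but the protocol allows that examination to Day 16, so a compliant late one drops out of Week 2

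*SAP*

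**What the plan says.** **When the early examination is done.** Footnote j to the protocol's Schedule of Procedures, repeated in SAP Appendix A, reads: "Prior to Visit 3 (Week 2) (between Days 7 and 14 [+2 days]), a standard ophthalmologic examination will be performed". Protocol 7.2 gives the same timing: "Prior to Visit 3 (Week 2) (between Days 7 and 14 [+2 days]), a standard ophthalmologic examination should be performed". SAP 6.4.2.8 gives a different range. There the standard examinations are "performed at Screening/Baseline, between post-dose days 7-15, and at end of treatment/Week 8".

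**How it is assigned to a visit.** SAP Addendum 5.1.1 replaces one row of main SAP Table 4 ("The analysis visit windows for the standard ophthalmologic examination at Visit 3 (Week 2) and Visit 4 (Week 4")). In Addendum Table 2 the row is: Week 2 = [2, 14], Weeks 4 and 6 = not applicable, Week 8 = ≥ 15 with no upper limit. Main SAP Table 4 had placed [2, 14] in the Week 4 column. The addendum moves it to Week 2 but keeps both cut-offs. Neither table assigns this examination by nominal visit.

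**How days are counted.** For dates on or after first dose, SAP 7.1.4 defines study day as "The assessment/event date minus the date of first dose of study drug, plus one". The day of first dose is therefore Day 1, the same scale as the visit days.

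**Where the mapping is used.** Of the ophthalmologic shift table, Addendum 5.3.1.1 says: "This summary will be presented by visit".

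**The concern.** The shift table is now split by visit, so the analysis window decides the column in which a result appears. If the Week 2 window is narrower than the period in which the protocol permits the Week 2 examination, some examinations done on time will not be counted at Week 2. Eye disorders are adverse events of special interest in this trial because of nonclinical findings of ocular phototoxicity (protocol 8.4). The early examination is thus a targeted safety check, and its table should contain every examination done as planned. Table 2 also sits awkwardly with its own header: the Week 2 column is headed Day 15 ± 2 days, yet Day 15 lies outside the window in that column.

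**Working it through.** No power, sample-size or error-rate figure is involved. The check maps each permitted day through Table 2 and then applies the record-selection rules of SAP 7.1.2.

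1. **Permitted days (footnote j, protocol 7.2).** Earliest Day 7; latest 14 + 2 = Day 16. Number of days: 16 − 7 + 1 = 10.

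2. **Mapping through Addendum Table 2.**
   - Days 7 to 14 (8 days): Week 2.
   - Days 15 and 16 (2 days): Week 8.

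3. **Does the requirement to precede Visit 3 close the gap?** Visit 3 is Day 15 ± 2, so Days 13 to 17. An examination on Day 15 precedes a Visit 3 on Day 16 or 17, and one on Day 16 precedes a Visit 3 on Day 17. Both days remain compliant when Visit 3 is late.

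4. **Does SAP 6.4.2.8 fit the window better?** Its upper limit of 15 post-dose days is Study Day 15 if read as a study day. If read as days elapsed since first dose, it is 15 + 1 = Study Day 16 under SAP 7.1.4. Both lie outside [2, 14].

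5. **What the table shows if a Visit 6 examination exists.** Both records fall in the Week 8 window. SAP 7.1.2 begins: "If there is a scheduled visit in the analysis window", and then uses that visit's data. The early examination appears only in a footnote to the schedule, and the SAP does not say whether it counts as scheduled.
   - If it does not, the Visit 6 record is used.
   - If both count as scheduled, the rule does not choose between them. Closeness to the scheduled day is the next criterion, although it is written for windows without a scheduled visit. It would also pick Visit 6: the early examination is 57 − 15 = 42 or 57 − 16 = 41 days from Day 57, against 0 to 2 days for an examination on Days 55 to 59.

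   On either reading nothing favours the early record, and Week 2 is empty for that subject.

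6. **What the table shows if no later standard eye examination exists.** The early examination is the only record in the Week 8 window. It is shown as the Week 8 result, 41 or 42 days before the nominal day.

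7. **Would a simple shift of the cut-off do?** With [2, 16] and ≥ 17, all ten permitted days map to Week 2, and Days 55 to 59 still map to Week 8. But subjects who stop early are encouraged "to complete all Visit 6 (Week 8) safety assessments (within 2 days of their last dose of study drug"), and Visit 6 includes a standard eye examination. An early-termination examination can therefore also fall on Day 15 or 16, and the simple shift would move it into Week 2. Study day alone cannot separate the two kinds of examination on those days.

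**The case against.** The case for leaving the table alone has weight. The early examination must precede Visit 3, whose nominal day is Day 15, so only a late Visit 3 exposes the gap. No safety information is lost: visit windows do not apply to listings (SAP 7.1.2), clinically significant eye abnormalities are listed by visit date (SAP 7.5.5.3), and treatment-emergent eye disorders are summarised as events of special interest (SAP 6.4.2.3 and 7.5.1). The Day 15 cut also keeps early-termination examinations from Day 15 onward out of Week 2, which is sensible. All of this stands, and it is why the point is minor. It does not remove the mismatch: the stated rule still puts an examination done within the protocol's limits into the wrong window.

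A reader might infer more, namely that a Day 15 or 16 examination generally appears as the Week 8 result or displaces the true one. The documents do not support that. Where a Visit 6 examination exists, no rule in SAP 7.1.2 prefers the early record, so the effect for such subjects is a missing Week 2 value. Nor should two of ten permitted days be read as a 20% rate of misfiling. It is a count of days, and the documents say nothing about how examinations are distributed over them.

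**Conclusion.** Wrong as written, and minor. Addendum Table 2 excludes from Week 2 two of the ten days on which the protocol permits the early standard eye examination. A subject examined on Day 15 or 16 has no Week 2 value in the by-visit shift table. The early result stands in for Week 8 only when there is no later standard eye examination. No efficacy result or hypothesis test is affected.

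The conclusion rests on reading the bracketed allowance in footnote j as extending the upper limit to Day 16, and on Visit 3 using its full window to Day 17.

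**What to change.** In Addendum Table 2, add a mapping note:

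- The early examination required by footnote j is assigned to Week 2 through Day 16.
- An end-of-treatment examination on Day 15 or later stays in Week 8, and the column is labelled Week 8/EOT because it includes early-termination examinations.

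Do not simply move the cut to [2, 16] and ≥ 17, for the reason in step 7 of the working. The note assumes that the database can tell the two examinations apart, which the documents do not show. If it cannot, the note should state that they overlap on Days 15 and 16 and how the overlap is resolved. Separately, reconcile the day range in SAP 6.4.2.8 with footnote j.

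The cost is one note under one table and one wording alignment. No examination or data collection is added.
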